#### **STUDY ENDPOINT EVALUATION: 12 MONTHS FOLLOWING THE INITIAL TREATMENT ADMINISTRATION**

- Photographic Documentation
- Measurement of mm of Clear Nail
- Percentage of Clinical Onychomycosis Involvement Determination
- Mycological Evaluation: InTray™ DM Culture

#### **TWO MONTHS AFTER STUDY ENDPOINT EVALUATION POST-TREATMENT EVALUATION**

- Photographic Documentation
- Measurement of mm of Clear Nail
- Percentage of Clinical Onychomycosis Involvement Determination
- Mycological Evaluation: InTray™ DM Culture

## **SAFETY AND CONFIDENTIALITY**

### **ADVERSE EVENTS**

At each evaluation and measurement point throughout the clinical study (as outlined in the STUDY EVALUATION TIMELINE section above), and at any other time throughout the duration of the clinical trial that is necessary, any and all potential adverse events reported by a subject or observed by an investigator will be recorded on the case report form, and subsequently evaluated by the investigator for its relation to the study procedure and whether or not any corrective action needs to be taken. All potential adverse events recorded will be applicably and appropriately reported to the governing IRB.

It is unlikely and not expected that any adverse events will result from implementation of this clinical study protocol. Prior clinical trials using Erchonia® low level lasers, including the LunulaLaser™ have not yielded any adverse events or reactions. However, potential adverse events that may feasibly occur from application of the Erchonia LunulaLaser™ and that will be specifically evaluated during scheduled adverse events evaluations include, but are not necessarily limited to: skin irritation, discoloring, rash, indentations and infection. Adverse events evaluation will be conducted for all toes/toenails on the study treated foot.

### **PRIVACY AND CONFIDENTIALITY**

Records for each subject in this clinical study will be maintained in separate files in a locked filing cabinet at the respective test site. The investigator at the test site will be responsible for ensuring that all records for a subject pertaining to his or her participation in the clinical study are stored in that subject's file at all times other than when information is being recorded on them.

Copies of all of the subject case report forms will be made and supplied to Regulatory Insight, Inc. and Erchonia Corporation. Regulatory Insight, Inc. and Erchonia Corporation will maintain these copies in a separate clinical study file that is kept in a locked filing cabinet on their respective premises. The original records will be maintained at the respective test sites.

Subjects' identities will be kept confidential by assigning each subject a subject ID upon acceptance into the study. The subject ID will comprise the investigator's two initials (first and last name initials) and a three-digit number that will be based upon the subject's order of entry into the clinical study. Each test site will be assigned a unique range of numbers. Test site #1 will be assigned numbers 001 to 100. Test site #2 will be assigned numbers 101 to 200, and so on. For example, the eighth subject to be enrolled at test site #2 with Principal Investigator John Black would have a subject ID of JB108. Neither the study Sponsor nor Regulatory Insight, Inc. will receive any additional identifying information about a subject and will therefore have no way of linking a subject ID to a particular subject and his or her results.

### **MONITORING OF THE CLINICAL STUDY**

Training, set-up and monitoring of the clinical study will be according to all of the applicable protocols and procedures contained within the Erchonia Corporation Clinical Trials Monitoring Plan, Version 2.0, March 15, 2015, contained in **Appendix E** of this clinical study protocol document.

Furthermore, monitors will train the study investigators to the following document: Erchonia Corporation Clinical Trial Investigator Responsibilities Procedure, Version 1.0, April 3, 2015, contained in **Appendix F** of this clinical study protocol document.

## **STATISTICAL ANALYSIS PLAN**

The aim of this study is to determine if there is a treatment effect of application of the Erchonia® LunulaLaser™ for individuals with onychomycosis of the great toenail.

### **PRIMARY EFFICACY OUTCOME EVALUATION**

The primary efficacy outcome measure in this study is the Complete Cure Rate at study endpoint.

Individual Subject Success Criteria: 'Complete Cure' criteria is defined as a subject/toenail satisfying both the 'Clinical Cure' and the 'Mycological Cure' criteria in order to be considered a study responder, defined as follows:

(i) Clinical Cure: Measurement of clear nail increase as the following:

- at least 12 mm increase in clear nail of the great toenail, with evidence of distal growth of the affected area, 12 months after the first treatment;  
or
- complete clearance 12 months after the first treatment if less than 12 mm distal nail was involved prior to treatment.

The response should be progressive in at least 2 sequential timepoints that are at least 3 months apart, with projected increase of at least 1 mm per month.

(ii) Mycologic Cure: Negative Fungal Culture results

Overall Study Success Criteria is defined as both of:

(i) a minimum 70% Clinical Cure Clear Nail Responder Rate;

AND

(ii) Among toenails which are deemed responders based on the Clinical Cure Clear Nail criteria, at least 80% will also demonstrate Mycological Cure.

### **STUDY END POINT EVALUATION**

The study end point evaluation at which Individual Great Toenail Success and Overall Study Success will be evaluated is at 12 months following initiation of the treatment administration phase.

### **HYPOTHESES**

- **Null Hypothesis**: The Responder Rate for subjects/toenails attaining Clinical Cure will be 70% or greater and 80% or more of those subjects will also attain Mycological Cure.
- **Alternative Hypothesis**: The Responder Rate for subjects/toenails attaining Clinical Cure will be less than 70% and/or fewer than 80% of those subjects will also attain Mycological Cure.

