## **PRIMARY EFFICACY OUTCOME STATISTICAL EVALUATION METHODS**

- **Intent to Treat (ITT) Principle:** Primary efficacy analysis will be according to the intent to treat (ITT) principle; wherein subjects will be included in the analysis if they had a valid Baseline Assessment visit.
- **Missing data** will be handled through *Last Observation Carried Forward (LOCF)*: by carrying forward the last recorded observation to fill in the subsequent missing value.

Subjects who drop out or are lost to follow-up will be considered as treatment failures (non-responders) in the statistical evaluation.

- **Per-Protocol Analysis** will also be performed for the set of all subjects who completed the study according to the full protocol.
- **Primary analysis of efficacy** according to *intent to treat* (ITT) analysis will be through determination of satisfaction of the Overall Study Success Criteria.

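### The SAP states its hypotheses the wrong way round and does not carry the sample-size confidence bound into the success rule, so the Complete Cure Rate has no benchmark in the SAP

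*Combined protocol and SAP*

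**What the plan says.** - **SAP, Hypotheses.** The null is "The Responder Rate for subjects/toenails attaining Clinical Cure will be 70% or greater and 80% or more of those subjects" also reaching Mycological Cure. The alternative is the complement: "The Responder Rate for subjects/toenails attaining Clinical Cure will be less than 70% and/or fewer than 80" per cent of them mycologically cured.
- **SAP, Primary Efficacy Outcome Evaluation.** "The primary efficacy outcome measure in this study is the Complete Cure Rate at study endpoint". A subject must meet both the clinical and the mycological criterion "in order to be considered a study responder, defined as follows". Overall success then has two parts, neither set on Complete Cure itself: "a minimum 70% Clinical Cure Clear Nail Responder Rate", and "Among toenails which are deemed responders based on the Clinical Cure Clear Nail criteria, at least 80% will also demonstrate Mycological Cure".
- **SAP, Primary Efficacy Outcome Statistical Evaluation Methods.** The ITT primary analysis "will be through determination of satisfaction of the Overall Study Success Criteria". No test, alpha or confidence bound is named. ITT takes in everyone with a valid baseline visit, and "Subjects who drop out or are lost to follow-up will be considered as treatment failures (non-responders) in the statistical evaluation".
- **Study Design, Rationale for sample size.** The plan takes a one-sided 95% lower bound around an observed response rate of 70% and asks that it be at least 50%, with 56% added in brackets. This gives 60 subjects, raised to 66 for a dropout of about one-twelfth. The response rate is not tied to an endpoint, and the 56% is not explained.

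**The concern.** A trial shows efficacy by rejecting a null in which the device does not work well enough. Here the null says that it does. Rejecting it would show failure, and not rejecting it would show nothing.

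The study has one arm (Study Treatment Group), so the decision rule carries the whole efficacy claim. The claim sought is eradication of the infection (Study Rationale and Justification), to be shown by clear nail together with negative mycology (Supporting Materials). That is Complete Cure. The SAP does not say what Complete Cure rate a passing result would have ruled out, or with what error.

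**Working it through.** **1. The plan's own sample-size figures.** The dropout step reproduces: 60 / (1 − 1/12) = 65.5, so 66. The bracketed 56% does not. At 42/60 (70%) the one-sided 95% lower bound is:

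- Wald: 0.70 − 1.645 × √(0.70 × 0.30 / 60) = 60.3%
- Wilson: 59.6%
- Exact (Clopper-Pearson): 58.8%

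None is 56%. The figure does equal 0.70 × 0.80, the product of the two success thresholds, but the plan does not make that link. So the sample-size section cannot show which endpoint or benchmark was meant.

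**2. What the reversed null would do if tested.** Take its clinical part (rate at least 70%) at one-sided 5% with n = 66. It is rejected only at 39/66 or fewer. A device with a true Clinical Cure rate of 60% would leave it standing 51% of the time.

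**3. Denominator.** Treatment starts on the day of the baseline visit, so a subject who drops out after that stays in the ITT set as a failure. With 66 enrolled, the ITT denominator is 66.

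**4. Smallest passing result at n = 66.**

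- Clinical Cure: 0.70 × 66 = 46.2, so 47 (71.2%; exact lower bound 60.7%).
- Culture-negative among those: 0.80 × 47 = 37.6, so 38.
- Complete Cure: 38/66 = 57.6%; exact lower bound 46.7%.

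A lower bound above 50% first occurs at 41/66 (51.3%); 40/66 gives 49.7%. Seven passing outcomes fall short (clinical/complete): 47/38, 47/39, 47/40, 48/39, 48/40, 49/40 and 50/40.

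**5. Worst-case false-pass rate.** Let X ~ Bin(66, pc) be clinical cures and M given X ~ Bin(X, pm) be those also culture-negative. The trial passes if X ≥ 0.7 × 66 and M ≥ 0.8X. The pass probability is maximised over all pc × pm equal to the benchmark.

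| Complete Cure benchmark | Worst case | At (pc, pm) |
|---|---|---|
| 50% | 5.7% | 0.659, 0.759 |
| 50% as the ITT rate, 6 of 66 dropouts counted as failures | about 5.1% | 0.736, 0.747 among completers |
| 56% | 24.8% | 0.699, 0.801 |

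If 50% was meant for Clinical Cure, every pass clears it, since the bound is already 60.7% at 47/66.

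With 60 as the denominator, the smallest pass is 42 clinical and 34 complete cures (56.7%, lower bound 45.2%), and the worst case is 8.3% against 50% and 29.8% against 56%. Those figures apply only to a reduced denominator such as per-protocol.

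**The case against.** **The plan does contain a bound.** A reader of the SAP alone might infer that the Complete Cure Rate has no benchmark, alpha or confidence bound anywhere. The documents do not support that. The sample-size rationale gives a one-sided 95% lower bound and a 50% figure for the response rate, and the SAP defines a study responder as a Complete Cure, so the bound may have been meant for the primary. But its 70% matches the Clinical Cure threshold, and it appears in neither the success criteria, the hypotheses nor the primary analysis. The gap is in the SAP's decision rule, not in the whole plan.

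**The reversal decides nothing.** A reader might infer that the device would be declared effective by failing to reject the null. The plan specifies no test of that null; success comes from the observed-rate criteria. Taken alone, the reversal is a drafting error. It still has to be corrected, because the hypotheses as written cannot support the claim.

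**The error is small.** This stands for a 50% benchmark: 5.7% at one unfavourable pair of rates, and about 5.1% with the planned dropouts. The 24.8% should not be read as the trial's false-positive rate. It requires 56% to be the Complete Cure null, whereas 56% is also the implied floor of the success rule, so 24.8% is essentially the chance of passing at that floor.

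**Conclusion.** The hypotheses are reversed, and no test of them could show efficacy. Success is read from observed component rates. The only confidence bound in the plan is left in the sample-size rationale, attached to an undefined response rate. In the SAP the named primary has no benchmark, only an implied observed floor of 0.70 × 0.80 = 56%.

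The size depends on what the sponsor meant:

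- **50% for Complete Cure:** a pass can leave the benchmark unproven (lower bound 46.7% at the smallest pass), but the excess over 5% is small.
- **56% for Complete Cure:** the worst case is 24.8%, but the plan does not say that this is the null.
- **50% for Clinical Cure:** every pass clears it, and the primary still has no benchmark.

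The case for changing the plan rests on the missing inferential rule in a single-arm trial, not on the largest error figure. The calculations assume an ITT set of 66 and independent binomial outcomes.

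**What to change.** 1. Restate the hypotheses as H0: ITT Complete Cure Rate ≤ p0 against H1: > p0, one-sided alpha 0.05.
2. Have the sponsor say which endpoint the sample-size bound applies to, explain the 56%, and fix p0 before outcome data are seen. The sample-size section already prints 50%.
3. In the success criteria and the primary analysis, keep both observed-rate thresholds and also require the exact one-sided 95% lower bound of the ITT Complete Cure Rate to exceed p0. State this as a bound, not a count, because the ITT number may not be 66. For reference, at n = 66 the bound alone needs 41 complete cures for p0 = 50% (type I error 3.2%) and 45 for p0 = 56% (2.9%).
4. Report the clinical, mycological and complete cure rates, each with its lower bound.

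The cost is SAP wording and some power; no new data are needed. Chance of success with 66 as the denominator:

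| True clinical / mycological rate | Dropouts | Current rule | p0 = 50% | p0 = 56% |
|---|---|---|---|---|
| 70% / 80% | none | 24.8% | 16.0% | 2.9% |
| 75% / 85% | none | 68% | 60% | 27% |
| 80% / 90% | none | 95.7% | 94.7% | 80% |
| 70% / 80% | 6 as failures | 5.2% | 2.4% | 0.2% |
| 75% / 85% | 6 as failures | 28% | 21% | 4.3% |
| 80% / 90% | 6 as failures | 68% | 65% | 36% |

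In the dropout rows the true rates are those of the 60 completers. The 2.9% is at a true Complete Cure rate of exactly 56%, so there it is the error rate and not lost power. The cost is modest at p0 = 50% and much larger at 56%, which the sponsor should weigh when fixing p0.

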## **PRIMARY EFFICACY OUTCOME STATISTICAL EVALUATION METHODS**

- **Intent to Treat (ITT) Principle:** Primary efficacy analysis will be according to the intent to treat (ITT) principle; wherein subjects will be included in the analysis if they had a valid Baseline Assessment visit.
- **Missing data** will be handled through *Last Observation Carried Forward (LOCF)*: by carrying forward the last recorded observation to fill in the subsequent missing value.

Subjects who drop out or are lost to follow-up will be considered as treatment failures (non-responders) in the statistical evaluation.

- **Per-Protocol Analysis** will also be performed for the set of all subjects who completed the study according to the full protocol.
- **Primary analysis of efficacy** according to *intent to treat* (ITT) analysis will be through determination of satisfaction of the Overall Study Success Criteria.

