Mycology testing was repeated for all enrolled subject toenails at 2 weeks post baseline evaluation. The results demonstrated the conversion from positive mycology to negative mycology as a result of the treatment administration with the Erchonia® LunulaLaser™ for all enrolled and treated study subject toenails.

Specifically, mycology testing results were as follows:

- *Baseline (Pre-Treatment) Evaluation:* Baseline results for all study toenails was a positive mycology for onychomycosis, denoted by detection of the presence of verifiable dermatophites consistent with onychomycosis. The culture results also indicated the positive presence of the *Trichophyton rubrum* strain for all samples. *Trichophyton rubrum* is the most common cause of onychomycosis in North America and Europe. The presence of

dermatophites was detected by day 3 or day 7, and the species identified as *T. rubrum* by day 7 or 14 in most cases, at which time the sample was destroyed.

- **Two Weeks Post-Baseline Evaluation:** All samples were found to have a negative mycology, consistent with the absence of onychomycosis. There was no change seen across all evaluation points, and the sample was destroyed following Day 21 evaluation.

The results summary of the culminating trial that resulted in the FDA's clearance for K153164 for the Erchonia® LunulaLaser™ is provided below:

➤ **A RETROSPECTIVE EVALUATION OF THE EFFECT OF THE ERCHONIA LUNULALASER™ ON THE INCREASE OF CLEAR NAIL IN PATIENTS WITH TOENAIL ONYCHOMYCOsis; Version 1.0; September 29, 2015**

**BACKGROUND:** The purpose of this study was to demonstrate through retrospective analysis the efficacy of the Erchonia LunulaLaser™, manufactured by Erchonia Corporation, for the increase of clear nail in patients with toenail onychomycosis, when applying the LunulaLaser™ to the toenail for 12 minutes one time per week for a total of 4 procedure administrations.

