#### Compensation

A subject will not be offered money or any other form of compensation to participate in the clinical study. However, he or she will also not be charged for the cost of the study treatments with the Erchonia® LunulaLaser™, the cost of the mycological lab testing or for the cost of any other directly-related evaluations or measurements that occur as part of his or her participation in the study.

Sample size

There will be 66 qualified subjects/great toenails enrolled in this clinical study across three test sites, approximately 22 subjects/great toenails per test site.

Rationale for sample size

The sample size of 66 subjects/great toenails was calculated based upon the 95% one-sided confidence interval (i.e. lower bound only) around the observed response rate of 70% being  $\geq$  50% (56%) yielding a pre-determined final sample size of 60 subjects/great toenails. From here, it is anticipated that about one-twelfth of subjects overall may withdraw or be terminated from the study prior to completion for various reasons. Therefore, the following formula is used to determine the final needed starting sample size for each procedure arm:

Final sample size = sample size  $\times$   $1/(1-d)$ ; where  $d$  = # expected dropouts/# subjects enrolled

Final sample size =  $60 \times 1/(1-0.082)$

Final sample size =  $60 \times 1/0.917 = 60 \times 1.091 = 66$  subjects

Therefore, a minimum starting sample size of 66 subjects is needed to insure that a sufficient number remains at the end of the treatment administration phase (60 subjects), assuming a drop-out rate of around one-twelfth, for a positive study outcome to be considered statistically valid, clinically meaningful and representative of the general population being sampled.

Subject Recruitment Advertisement

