By design of the device, it is not possible for the subject to move the foot's position to any significant degree that would impact the intended exposure to the laser procedure, particularly considering that the laser beam is designed to cover the entire treated toe region. The exception would be if the subject withdrew his or her foot entirely from the laser device mid-treatment administration, in which case, the foot would be re-inserted at once and the remaining minutes of exposure completed such that the total maximum exposure time in one session would not ever exceed the pre-determined 12-minutes. If the subject was unable or refused to re-insert his or her foot for any reason, the subject would be disqualified from further study participation at that time.

6. The subject removes his or her foot from the Erchonia LunulaLaser™.
7. The laser treatment administration is complete.
8. The subject removes the safety glasses, and the treatment procedure administration protocol is completed.

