#### **AT EACH TREATMENT ADMINISTRATION VISIT COMMENCING WITH THE FOURTH WEEKLY TREATMENT ADMINISTRATION (END OF WEEK 4, MONTHS 3, 5, 7, 9, AND 11)**

- Photographic Documentation
- Measurement of mm of Clear Nail
- Percentage of Clinical Onychomycosis Involvement Determination
- Mycological Evaluation: InTray™ DM Culture

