#### **TWO MONTHS AFTER STUDY ENDPOINT EVALUATION POST-TREATMENT EVALUATION**

- Photographic Documentation
- Measurement of mm of Clear Nail
- Percentage of Clinical Onychomycosis Involvement Determination
- Mycological Evaluation: InTray™ DM Culture

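### For a subject still in the study, last observation carried forward (LOCF) lets an earlier photograph or culture stand as cure at 12 months; score an unobserved Month-12 result as non-response instead

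*Combined protocol and SAP*

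**What the plan says.** Under Primary Efficacy Outcome Statistical Evaluation Methods, the SAP includes in the ITT analysis every subject with a valid baseline visit and fills missing data by LOCF: "by carrying forward the last recorded observation to fill in the subsequent missing value". It sets no limit on the age of the carried value and no visit window, and makes no exception for photograph or culture. The next sentence gives a different rule for subjects who leave: "Subjects who drop out or are lost to follow-up will be considered as treatment failures (non-responders) in the statistical evaluation". The order of the two rules is not stated.

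The Primary Efficacy Outcome Evaluation and Study End Point Evaluation sections fix cure at 12 months after the first treatment. Clinical cure is a gain of at least 12 mm of clear nail, or complete clearance where less than 12 mm was involved, with a progression condition over visits at least 3 months apart. Mycological cure is a negative culture. Success needs a clinical cure rate of at least 70%, and mycological cure in at least 80% of the clinical responders.

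Photographs and cultures are taken at treatment visits "COMMENCING WITH THE FOURTH WEEKLY TREATMENT ADMINISTRATION (END OF WEEK 4, MONTHS 3, 5, 7, 9, AND 11", at Month 12, and again at Month 14 ("TWO MONTHS AFTER STUDY ENDPOINT EVALUATION POST-TREATMENT EVALUATION"). The Secondary Efficacy Outcome Evaluation section states no missing-data rule for its week-52 endpoints.

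**The concern.** The natural reading of the two rules is failure for subjects who leave and LOCF for gaps in subjects who stay. A retained subject who misses Month 12, or whose Month-12 culture is unusable, is then judged on the last earlier visit. The result enters the 12-month cure rate although nothing was observed at 12 months.

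Two routes can favour the device: a nail that was completely clear earlier, or a culture that was negative earlier, where the state has since reversed. Reversal is a possibility that the plan itself allows for, since Safety Analyses provides for a re-infection rate. The sponsor's earlier study, summarised under Supporting Materials, reports of its cultures two weeks after baseline: "All samples were found to have a negative mycology, consistent with the absence of onychomycosis". That shows that negative cultures can appear early. It does not show how many last.

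There is no control arm, and success is a count against two fixed thresholds. An imputation error therefore goes straight into the device's cure rate and is not offset by a similar error in a comparison group.

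**Working it through.** **Inputs.** Enrolment 66, evaluable 60 and dropout of about one-twelfth (Rationale for sample size); thresholds 70% and 80% (Primary Efficacy Outcome Evaluation); visit times (Study Evaluation Timeline and Measures). Two inputs are assumptions: the number of retained subjects without a Month-12 result (1 to 3), for which the documents give no figure, and the true rates used in the probabilities.

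**The plan's own figure.** 60 / (1 − 1/12) = 65.45, rounded up to 66, as stated.

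**Thresholds as counts.**
- Clinical: 0.70 × 66 = 46.2, so 47 are needed. 46/66 = 69.7% fails and 47/66 = 71.2% passes.
- Mycological, at the minimum of 47 clinical responders: 0.80 × 47 = 37.6, so 38 are needed. 37/47 = 78.7% fails and 38/47 = 80.9% passes.

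One carried result decides the verdict only when the count sits at one of these edges.

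**Direction on the 12 mm route.** At 1 mm per month, the rate named in the progression condition, the gain is 9 mm at Month 9 and 11 mm at Month 11. Carried forward, both fail. Reaching 12 mm by Month 11 needs 12/11 = 1.09 mm per month. Here LOCF may work against the device.

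**Progression condition.** It limits LOCF only in part. Months 7 and 11 are 4 months apart, so two earlier visits could meet it with no Month-12 value.

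**Effect on the mycological criterion.** Let c of the 47 responders lack a Month-12 culture, and let observed cultures be negative with probability 0.80. If all c are carried as negative, the criterion is met when X ≥ 38 − c, with X ~ Bin(47 − c, 0.80). If missing counts as not cured, it is met when X ≥ 38.

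| c | Observed negatives needed, all carried as negative | Chance | Observed negatives needed, missing = not cured | Chance |
|---|---|---|---|---|
| 0 | 38/47 (80.9%) | 52.9% | 38/47 (80.9%) | 52.9% |
| 1 | 37/46 (80.4%) | 55.9% | 38/46 (82.6%) | 41.2% |
| 2 | 36/45 (80.0%) | 58.8% | 38/45 (84.4%) | 29.7% |

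For c = 3 the observed negatives needed are 35/44 (79.5%) and 38/44 (86.4%).

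If the one carried culture is itself negative at the true rate, the chance is 0.80 × 0.559 + 0.20 × 0.412 = 0.529, the same as with complete data. LOCF inflates the chance only so far as carried cultures are negative more often than Month-12 cultures would be.

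**Effect on the clinical criterion.** With N = 66 and a true cure rate of 70%, the chance of at least 47 cures is 47.5% with complete data. With one missing result it is 50.7% if carried as cure and 40.0% if counted as failure. With three it is 57.2% and 25.8%. The carried-as-cure figures are worst cases, because the 12 mm route tends the other way.

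**The case against.** The strongest reply is that the main source of missing data is already handled conservatively. The failure sentence follows directly after LOCF and is the more specific rule, so it naturally governs dropouts. A reader might infer that the two rules contradict each other, or that LOCF overrides the failure rule, with a swing of (66 − 60)/66 = 9.1 percentage points. The documents do not support that: they leave an order unstated and no more. Nor are terminated subjects clearly outside the failure rule. The sample-size rationale expects that "about one-twelfth of subjects overall may withdraw or be terminated from the study prior to completion" and then speaks of "assuming a drop-out rate of around one-twelfth", so it already counts termination as dropout. The exit left unnamed is the narrow one under Treatment Administration Protocol, for a subject who cannot or will not put the foot back: "the subject would be disqualified from further study participation at that time". This part is a wording matter.

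A reader might also infer from the earlier study that a carried culture would be negative whatever the Month-12 state. That study cultured at two weeks. In this trial the last value would ordinarily come from Month 11, one month before the endpoint, and the documents give no rate of reversal between the two visits.

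It is also fair to say that LOCF's own effect is small and shrinks away from the threshold. At a true negative rate of 90%, one missing culture gives 98.4% with complete data, 98.6% if carried as negative and 96.4% if counted as not cured. The planned per-protocol analysis and the responder rates by visit would partly expose reliance on carried values.

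All of this stands, and it limits the weight of the point. It does not remove it. Nothing in the SAP prevents a 12-month cure from being credited without a 12-month observation, and neither of the planned checks replaces the primary result.

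**Conclusion.** The point holds as a recommended change of moderate weight. The SAP's LOCF rule allows a retained subject's result from Week 4 to Month 11 to count as cure at Month 12. In the worst case, with every carried culture negative, each missing culture raises the chance of meeting the mycological criterion by about 3 points (53% to 56%, then 59%). There is no inflation if carried cultures are negative at the true rate, and on the 12 mm route the effect may run against the device. The falls to 41% and 30% in the table are the cost of scoring missing as not cured and should not be read as the effect of LOCF.

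The size rests on an assumed 1 to 3 affected subjects, on exactly 47 clinical responders and on a true rate at the threshold. The documents do not support a claim that LOCF will materially change the outcome. They do show that the rule does not match an endpoint defined at 12 months.

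**What to change.** In Primary Efficacy Outcome Statistical Evaluation Methods:

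1. Score any ITT subject without an observed Month-12 result, within a visit window that the sponsor states, as a non-responder. Count a clinical responder with no valid Month-12 culture as not mycologically cured. State in Secondary Efficacy Outcome Evaluation that the same rule applies to the first two secondary endpoints.
2. Bar imputed values from meeting the progression condition. What sequential visits at least 3 months apart means, when scheduled visits are at most 2 months apart, is a separate question and is left open here.
3. Report as sensitivity analyses LOCF, observed cases, and the observed Month-14 result in place of a missing Month-12 result, beside the per-protocol analysis already planned.
4. As a minor wording point, state that the failure rule prevails over LOCF and also covers terminated and disqualified subjects.

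This extends the plan's own treatment of dropouts and needs no new visits or data. The cost is a slightly less favourable cure rate. In the example above, one missing culture counted as not cured lowers the chance of meeting the mycological criterion from 53% to 41%, and two lower it to 30%.
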